4.2.2 Radiation Treatment Visits

Lazanda will be self-administered by the subject while attending their visit to the radiation treatment center, and will be monitored closely by the clinic staff and study coordinator. Therefore, the chance for a missed dose is rare. However, should a subject miss a Lazanda dose prior to treatment fraction, he or she will be instructed to take the dose as soon as it is remembered on the same day prior to radiation.

The dose used as pre-medication prior to any radiation therapy fractions is as described in the titration schema listed above in section 4.2.1 and described in Table 1.

If a patient takes less than the minimal effective dose of Lazanda, they should be monitored closely for evidence of opioid withdrawal symptoms and reversal of central analgesic effects. In cases of known or suspected overdose, symptomatic treatment as well as monitoring of vital functions will be performed. In cases of severe intoxication, intensive care procedures will be completed. Close medical supervision and monitoring will be continued until the patient recovers.

Subjects will be required to record each self-administered dose of Lazanda on a Study Drug Diary (**Appendix H**) from the time of the radiation simulation visit through the end of radiation therapy. Details of Lazanda administration, including date and time of administration as well as number of sprays administered and total daily dose will be recorded by the subject on the Study Drug Diary.

Lazanda will be dispensed to the patient in nasal spray bottle format, within a child-resistant outer container. The child-resistant container should be opened just prior to initial product use. Subjects will be instructed to replace the bottle in the child-resistant container and out of reach of children between doses. Subjects will also be instructed to avoid consumption of grapefruit or grapefruit juice as this is a potent inhibitor of the CYP3A4 enzyme.

There are additional no requirements for monitoring of vital signs or other parameters following Lazanda administration. Treatment with Lazanda does not require that any pre-treatment parameters be met prior to dispensing and/or administration. However, subjects will be advised not to drive during study participation and must be accompanied to all treatments.

Any adverse events or serious adverse events resulting from known or suspected overdose will be reported according to instructions in **Section 7.6** of the protocol.

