1.2 Study Agent(s)

Fentanyl pectin nasal spray (Lazanda is commercially available and indicated for the management of BTCP in adults 18 years of age and older who are already receiving and who are tolerant to opioid therapy for treatment of cancer pain. Lazanda's mechanism of action is a pure opioid agonist. Lazanda pharmacokinetics in healthy subjects and in patients with a history of allergic rhinitis have been published⁹⁻¹¹. In summary, median (range) time to maximum concentration (T_{max}) is 15-30 (10.2-60) minutes. After single dose administration, maximum concentrations (C_{max}) ranged from 0.3 to 1.74 ng/mL; elimination half-life is approximately 5.5 to 9.7 hours. Fentanyl is metabolized in the liver and intestinal mucosa to norfentanyl by cytochrome P450 (CYP) 3A4. Concomitant use of Lazanda with a CYP3A4 inhibitor (**Appendix B**) may result in a potentially dangerous increase in fentanyl plasma concentrations, which could prolong adverse drug effects. Patients receiving Lazanda who begin or increase the dose of a CYP3A4 inhibitor drug should be carefully monitored for signs of opioid toxicity. More than 90% of fentanyl is eliminated via biotransformation to N-dealkylated and hydroxylated inactive metabolites. The metabolites are mainly excreted in urine.

In a randomized, double-blind, placebo controlled study, cancer patients (n=73) were titrated to an effective pain relief dose (100, 200, 400, or 800 mcg) of Lazanda. The sum of pain intensity difference at 30 minutes (SPID₃₀) was 6.57 ± 4.99 (mean \pm SD) and 4.45 ± 5.51 for Lazanda versus placebo, respectively (p<0.05). Other secondary pain measures including pain intensity (PI) scores, pain intensity difference (PID), and pain relief were all statistically significant compared to placebo at 10, 15, 30, 45, and 60 minutes after administration. Decreases in pain intensity by 2 or more were seen in 49% and 63% of patients 15 and 30 minutes after fentanyl pectin nasal spray administration.¹² These results, specifically a statistically significant higher SPID and decreased pain intensity, are consistent in another randomized, placebo controlled, study in cancer patients (n=83).¹³

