Lazanda titration should be done with caution in patients with chronic obstructive pulmonary disease or preexisting medical conditions predisposing them to respiratory depression and in patients susceptible to intracranial effects of CO₂ retention. Caution should also be used in patients on central nervous system (CNS) depressants and potent CYP3A4 inhibitors.

The minimal effective intranasal dose from the radiation therapy simulation will be the dose used as pre-medication prior to any further radiation therapy fractions (up to 10 fractions). Lazanda should be administered 15 (T-15) minutes prior to laying on the hard surface for each simulation visit. If the response to the titrated Lazanda dose markedly changes, an adjustment of dose may be necessary to ensure that an appropriate dose is maintained as deemed by the investigator.

Subjects will be instructed on the proper use of Lazanda as follows:

- 1) Prime the device before use by spraying into the pouch (4 sprays in total). If study drug has not been used for 5 days, re-prime by spraying once.
- 2) Insert the nozzle of the Lazanda bottle a short distance (about ½ inch) into the nose and point towards the bridge of the nose, tilting the bottle slightly.
- 3) Press down firmly on the finger grips until hearing a “click” and the number in the counting window advances by one.

Subjects will also be advised that the fine mist spray is not always felt on the nasal mucous membrane and to rely on the audible click and advancement of the dose counter to confirm a spray have been administered.

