4.4 Permitted concomitant therapy

Patients must remain on around-the-clock opioids when taking Lazanda. Throughout the study, many participants will be receiving a long-acting opioid for control of background pain and an immediate-release opioid as needed (“prn”) for breakthrough pain, although some may be receiving only a short-acting opioid on a scheduled basis. If the participant experiences more than 4 episodes of breakthrough pain per day while on study, the investigator will re-evaluate and appropriate titrate short and long-acting opioids per standard of care. Changes in the opioid regimen may be made to ensure appropriate pain control. Any changes to the maintenance opioid dosing regimen will be recorded. Concomitant non-opioid analgesics will be permitted, but investigators will be encouraged to maintain such drugs at stable doses on-study.

Fentanyl is metabolized in the liver and intestinal mucosa to norfentanyl by CYP3A4. Concomitant use of Lazanda with a CYP3A4 inhibitor (**Appendix B**) may result in a potentially dangerous increase in fentanyl plasma concentrations, which could prolong adverse drug effects. Patients receiving Lazanda who begin or increase the dose of a CYP3A4 inhibitor drug is permitted, but should be carefully monitored for signs of opioid toxicity.

Medications required to treat adverse events and manage cancer symptoms, concurrent stable disease (e.g., controlled hypertension) and supportive care agents such as erythropoietin, granulocyte growth factors, or blood transfusion, and pain medications are allowed. The patient needs to notify the investigational site about any new medications he/she takes after the start of the study medication. All medications (other than study drug) and significant non-drug therapies (including physical therapy and blood transfusions) administered after the patient starts treatment with study drug must be recorded in the patient’s medical record.

Palliative and supportive care for disease-related symptoms, including pain medications, is permitted. Hematopoietic growth factors such as erythropoietin or G-CSF are allowed if clinically indicated only after the first 28 days of study treatment. Use of growth factors will follow NCCN guidelines.

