Appendix B. Strong and Moderate CYP3A4 Inhibitors

Strong CYP3A4 inhibitors allowed during study and include but are not limited to the following:

[figure not shown]
- Boceprevir
- Clarithromycin
- Conivaptan
- Grapefruit juice
- Indinavir
- Itraconazole
- Ketoconazole
- Lopinavir/ritonavir
- Mibefradil
- Nefazodone
- Nelfinavir
- Posaconazole
- Ritonavir,
- Saquinavir
- Telaprevir
- Telithromycin
- Voriconazole

Moderate CYP3A4 inhibitors are allowed during study and include but are not limited to the following:

- Amprenavir
- Aprepitant,
- Atazanavir,
- Ciprofloxacin,
- Darunavir/ritonavir,
- Diltiazem,
- Erythromycin,
- Fluconazole,
- Fosamprenavir,
- Grapefruit juice,
- Imatinib,
- Verapamil

Please refer to the U.S. Food and Drug Administration website, *Drug Development and Drug Interactions: Table of Substrates, Inhibitors and Inducers*, for additional information:
<http://www.fda.gov/Drugs/DevelopmentApprovalProcess/DevelopmentResources/DrugInteractionsLabeling/ucm093664.htm>

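### Section 4.2.2 tells subjects to avoid grapefruit juice, but Appendix B lists it as permitted on study, and nothing in the visible text reconciles the two

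*Combined protocol and SAP*

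**What the plan says.** **Instruction to subjects.** Section 4.2.2 (Radiation Treatment Visits) has subjects "instructed to avoid consumption of grapefruit or grapefruit juice as this is a potent inhibitor of the CYP3A4 enzyme".

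**Appendix B.** It holds two lists. The first is headed "Strong CYP3A4 inhibitors allowed during study and include but are not limited to the following", the second "Moderate CYP3A4 inhibitors are allowed during study and include but are not limited to the following". The entry "Grapefruit juice" stands in both.

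**Where Appendix B is used.** Section 1.2 warns that taking Lazanda with a CYP3A4 inhibitor "may result in a potentially dangerous increase in fentanyl plasma concentrations" and cites Appendix B for the inhibitors meant. Section 4.4 repeats the warning with the same citation, then says that for patients on Lazanda to "begin or increase the dose of a CYP3A4 inhibitor drug is permitted, but should be carefully monitored for signs of opioid toxicity".

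**Other relevant text.** On titration, Section 4.2.1 says: "Caution should also be used in patients on central nervous system (CNS) depressants and potent CYP3A4 inhibitors". Section 4.2.2 says that self-administration at the treatment centre "will be monitored closely by the clinic staff and study coordinator". The same section adds that no further checks of vital signs or other parameters are required after a dose. Section 4.5 (Prohibited concomitant therapy) mentions neither grapefruit nor CYP3A4 inhibitors.

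**The concern.** Two current parts of one document give different answers to a simple question: may a subject on intranasal fentanyl drink grapefruit juice? Section 4.2.2 says no. Appendix B, read alone, says yes, twice.

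The appendix is the natural place for a nurse, pharmacist or coordinator to look, because both interaction warnings point there. Someone who answers a subject's question from it could undo the 4.2.2 instruction, or see no reason to reinforce it. The drug is an opioid, and the protocol itself treats CYP3A4 inhibition as a possible cause of dangerously raised fentanyl levels. At stake is consistent safety advice to subjects. The statistical results are not in question.

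**Working it through.** The plan states no figure on this point, and the only arithmetic is a count of list entries. The rest is a comparison of texts.

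**1. Do the two rules meet on the same item?** Yes. Section 4.2.2 covers grapefruit and its juice. Appendix B names the juice.

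**2. How many lines conflict?**

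| Appendix B list | Entries | Grapefruit juice entries |
|---|---|---|
| Strong | 17 | 1 |
| Moderate | 12 | 1 |
| Total | 17 + 12 = 29 | 1 + 1 = 2 |

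So 2 of 29 lines contradict Section 4.2.2. Grapefruit juice is the only entry that appears under an identical name in both lists, which leaves 29 − 1 = 28 distinct entries. (Ritonavir alone, with lopinavir and with darunavir are counted as three different entries.)

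**3. Does anything reconcile them?** In the visible text grapefruit appears only in Section 4.2.2 and Appendix B. Sections 1.2 and 4.4 cite the appendix without an exception, and Section 4.5 is silent.

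**4. Does the permission in Section 4.4 make the appendix wording harmless?** Not clearly. Its monitoring condition concerns patients who start, or raise the dose of, an inhibitor *drug*. A juice fits that poorly. The concomitant-medication record (5.1.4) and the medication diary (5.1.11.3, Appendix E) cover medicines, vitamins, herbal remedies and supplements, with no prompt for food or drink. The instruction to avoid grapefruit is therefore the only grapefruit-specific safeguard in the visible text.

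**5. How firm is that safeguard?**
- *Timing.* Section 8.1 has subjects taught before the first dose how to use the product properly, with reference to Section 4.2. The teaching introduced in those terms, in Section 4.2.1, is the three device steps: priming, inserting the nozzle and pressing. The grapefruit sentence stands in 4.2.2, under treatment visits, whereas the first dose is given at simulation. Section 8.1 can be read as covering all of 4.2, but the text does not settle it.
- *Monitoring.* The close observation described in 4.2.2 is offered as the reason why a missed dose should be rare. It is not a plan for detecting toxicity, and the section sets no additional post-dose monitoring.

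**6. Does any analysis depend on it?** No. The PID₁₅ definition, the mixed model, the BPI-sf analysis, the treatment-time comparison and the sample size in Section 9 make no use of CYP3A4 status.

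**The case against.** The best defence is that the two texts do different jobs. Section 4.2.2 advises subjects. Appendix B identifies a class of inhibitors, and its headings may mean only that these are not prohibited. An item can be advised against without being a protocol violation, and a specific instruction would ordinarily prevail over a general list. This softens the conflict but does not remove it: the headings go beyond classification, declare the entries permitted and except nothing.

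A second defence is that the consequence is slight. The instruction meant for subjects is already the safe one, Section 4.2.1 asks for caution with potent inhibitors during titration, and the idea that staff would pass on the wrong rule is a possibility, not an observation. All of this stands, and it is why the point ranks low.

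Third, the consent pages were removed before review, and the Investigator's Brochure and package insert are not available here. Any of them may carry grapefruit advice, so the claim of a single safeguard is limited to the visible text.

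A reader might also infer that the double listing matters because it leaves the strength class of grapefruit juice unclear. The documents do not support that. Section 4.4 applies one rule to all CYP3A4 inhibitors, and no dose, eligibility or monitoring rule turns on strong versus moderate. The only mention of potency as a trigger is the general caution in 4.2.1, and 4.2.2 already calls grapefruit potent.

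**Conclusion.** The inconsistency is real and the protocol is wrong as written: avoid in Section 4.2.2, permitted in 2 of the 29 lines of Appendix B, with no reconciling text in view. It is a low-severity safety inconsistency that is worth correcting because the correction is nearly free.

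The count measures the text error only. A reader might infer that subjects face a material risk of fentanyl toxicity from this wording. The documents give no rate of grapefruit use and no size for its effect on fentanyl exposure, so they do not support that, and no estimate is offered. Nor should the reassurance be overstated: the text fixes no clear time before the first dose for the instruction and adds no post-dose monitoring.

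The conclusion assumes that Section 4.2.2 expresses the sponsor's intent, since it gives a reason for its rule, and that the removed and unavailable materials do not settle the matter. No endpoint, sample size or analysis is affected.

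**What to change.** Keep the rule in Section 4.2.2. In Appendix B, take grapefruit juice out of the two permitted lists and put in their place one entry, set apart from both, marked *avoid, see 4.2.2*. Do not simply delete the entries: Sections 1.2 and 4.4 rely on this list to identify interacting agents, and deletion would remove grapefruit from the place where staff look for it.

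The cost is two lines in one appendix, submitted to the IRB with an amendment under Section 10.10. No new visits, data or analyses are needed, and no other section has to change.

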4.3 Pre-Medications

There are no required pre-medications on this study.

4.4 Permitted concomitant therapy

Patients must remain on around-the-clock opioids when taking Lazanda. Throughout the study, many participants will be receiving a long-acting opioid for control of background pain and an immediate-release opioid as needed (“prn”) for breakthrough pain, although some may be receiving only a short-acting opioid on a scheduled basis. If the participant experiences more than 4 episodes of breakthrough pain per day while on study, the investigator will re-evaluate and appropriate titrate short and long-acting opioids per standard of care. Changes in the opioid regimen may be made to ensure appropriate pain control. Any changes to the maintenance opioid dosing regimen will be recorded. Concomitant non-opioid analgesics will be permitted, but investigators will be encouraged to maintain such drugs at stable doses on-study.

Fentanyl is metabolized in the liver and intestinal mucosa to norfentanyl by CYP3A4. Concomitant use of Lazanda with a CYP3A4 inhibitor (**Appendix B**) may result in a potentially dangerous increase in fentanyl plasma concentrations, which could prolong adverse drug effects. Patients receiving Lazanda who begin or increase the dose of a CYP3A4 inhibitor drug is permitted, but should be carefully monitored for signs of opioid toxicity.

Medications required to treat adverse events and manage cancer symptoms, concurrent stable disease (e.g., controlled hypertension) and supportive care agents such as erythropoietin, granulocyte growth factors, or blood transfusion, and pain medications are allowed. The patient needs to notify the investigational site about any new medications he/she takes after the start of the study medication. All medications (other than study drug) and significant non-drug therapies (including physical therapy and blood transfusions) administered after the patient starts treatment with study drug must be recorded in the patient’s medical record.

Palliative and supportive care for disease-related symptoms, including pain medications, is permitted. Hematopoietic growth factors such as erythropoietin or G-CSF are allowed if clinically indicated only after the first 28 days of study treatment. Use of growth factors will follow NCCN guidelines.

4.5 Prohibited concomitant therapy

Unless there is a need for urgent intervention, additional medication for pain control will not be allowed without prior approval from the principal investigator. This includes over-the-counter treatments for pain. Concomitant use of a monoamine oxidase inhibitor is prohibited. Other investigational therapies must not be used while the patient is on the study. If such agents are required for a patient then the patient must be discontinued from the treatment portion of the study.

4.6 Radiation Therapy

Subjects will undergo radiation therapy simulation procedures and receive palliative radiation during this trial according to UCSD Radiation Oncology standard procedure, and according to the radiation treatment plan as determined by their radiation oncologist.

4.7 Toxicities and Dosing Delays/Dose Modifications

Any patient who receives treatment on this protocol will be evaluable for toxicity. Each patient will be assessed for the development of toxicity according to the NCI CTCAE, version 4.03.

Dose adjustments should be made according to the system showing the greatest degree of toxicity.

Table 2: Dose Modifications for Lazanda-Related Nausea and/or Vomiting

Nausea/Vomiting	Management for Lazanda
≤ Grade 1	No action required.
Grade 2	Hold until ≤ Grade 1. Resume at same dose.
Grade 3	Hold until < Grade 2. Resume at same dose.
Grade 4	Off protocol therapy
Recommended symptom management: Treatment with a dopamine antagonist antiemetic (e.g. metoclopramide, prochlorperazine, haloperidol) and strong consideration of premedication prior to next Lazanda dose.	

Table 3: Dose Modifications for Lazanda-Related Constipation

Constipation	Management for Lazanda
≤ Grade 1	No action required.
Grade 2	Hold until ≤ Grade 1. Resume at same dose.
Grade 3	Hold until < Grade 2. Resume at same dose.
Grade 4	Off protocol therapy
Recommended symptom management: Opioid-induced constipation is managed with stimulant laxatives (senna, bisacodyl) with or without an osmotic laxative (e.g. polyethylene glycol).	

Table 4: Dose Modifications for Lazanda-Related Urinary Retention

Urinary Retention	Management for Lazanda
≤ Grade 1	No action required.
Grade 2	Hold until ≤ Grade 1. Resume at same dose.
Grade 3	Hold until < Grade 2. Resume at same dose
Grade 4	Off protocol therapy
Recommended symptom management: Evaluation including physical exam, ultrasound bladder scan, and consideration of a time-limited trial of catheter placement.	

Table 5: Dose Modifications for Lazanda-Related Somnolence

Somnolence	Management for Lazanda
≤ Grade 1	No action required.
Grade 2	Hold until ≤ Grade 1. Resume at same dose.
Grade 3	Hold until < Grade 2. Resume at half dose.
Grade 4	Off protocol therapy
Recommended symptom management: Urgent evaluation by investigator and medical management per standard of care.	

Patients requiring a delay of greater than 2 weeks or greater than 2 dose reductions in Lazanda dose for any toxicity should discontinue protocol therapy.

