In comparison to morphine sulfate IR, higher PID scores and a greater proportion of patients achieving >33% or >2 point pain intensity score reduction have been reported with Lazanda[®].^{14,15} In one study, pain intensity difference at 15 minutes (mean \pm SD) was 3.0 ± 0.2 and 2.7 ± 0.2 (p<0.05) for Lazanda and morphine sulfate IR, respectively.¹⁵ Decreases in pain intensity by 2 or more was seen in 52.4% and 45.4% of patients (p<0.05) 10 minutes after Lazanda and morphine sulfate IR administration.¹⁴ In another study, PI scores after 5 minutes

(5.6 vs. 5.8) and after 20 minutes (3 vs 3.4) were significantly lower for Lazanda versus intranasal fentanyl. Five minutes after administration, more patients experienced a >33% pain intensity reduction (~13% vs. <5%; $p < 0.05$), while at 20 minutes after administration, more patients experiences a >50% pain intensity reduction (~71% vs. ~55%; $p < 0.05$) with Lazanda.¹⁶

Common adverse events are drowsiness, nausea, vomiting, and constipation, with most these symptoms mild to moderate in severity. Nasal symptoms, including obstruction, discomfort, itching, sneezing, dryness, and crusting have also been mostly reported as mild and moderate in severity.¹²⁻¹⁷ Ninety-nine serious adverse events have been reported in 3 studies, with 25 of these deemed related to fentanyl pectin nasal spray.^{12,15,17} Two deaths possibly related to fentanyl pectin nasal spray have been reported.^{15,17} In one death, the patient developed cyanosis, loss of consciousness, and upper airway obstruction after an apparent unintentional overdose during a breakthrough pain episode.¹⁷

The initial starting dose for this study will be Lazanda 100 mcg prior to radiation therapy simulation. A 100 mcg dose is the initial dose of Lazanda for all patients as detailed in the product package insert. Lazanda dose titration will follow the guidelines as indicated in the product package insert from the baseline visit through the end of radiation therapy. If the subject does not experience relief after 30 minutes, he or she may take another 100 mcg but must wait at least 2 hours from the first spray before administering this second 100 mcg dose.

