4.2.1 Radiation Simulation Visit(s)

To determine an individual patient's effective and tolerable Lazanda dose, each subject will undergo dose titration during the radiation simulation visit. Lazanda dose for all subjects on study, including those switching from another fentanyl product, will be determined according to the following procedures:

- 15 minutes prior (T-15) to beginning the radiation therapy simulation, subjects will receive an initial dose of 100 mcg (1 spray) of Lazanda in one nostril prior to lying on the CT simulation hard surface.
- If adequate analgesia is obtained within 30 minutes of administration of the 100-mcg single spray, subsequent pain episodes will be treated with this dose.
- If the subject does not experience relief after 30 minutes, he or she may take another 100 mcg in the opposite nostril **but must wait at least 2 hours** (i.e., T-15 + 2 hours) from the first spray before administering this second 100 mcg dose. The subject may delay or reschedule the simulation (within a 14 days period) or radiation delivery to achieve the adequate pain control dose.
- If adequate analgesia is still not achieved, the subject will continue to dose escalate in a step-wise manner at a minimum of 2 hours between each subsequent escalation until adequate analgesia with tolerable side effects is achieved. A maximum of 4 doses or 400 mcg allowed per day.
- Dose titration steps are further detailed in **Table 1**.

Table 1: Lazanda Dose Titration Steps

Lazanda Dose	Using
100 mcg	1 x 100 mcg spray
200 mcg	2 x 100 mcg spray (1 in each nostril)
400 mcg	4 x 100 mcg spray (2 in each nostril, alternate nostrils) or 1 x 400 mcg spray

Each bottle contains a total of 8 sprays. Lazanda bottles come in 100 mcg or 400 mcg dose. If using dose of 100 mcg with the 100-mcg spray, the patient would have total of 8 doses in a single bottle. If using dose of 200 mcg with the 100-mcg spray, the patient would have total of 4 doses in a single bottle. If using dose of 400 mcg with the 100-mcg spray, the patient would have total of 2 doses in a single bottle. Alternately, if using a bottle of the 400-mcg spray at a dose of 400 mcg, the patient would have total of 8 doses in a single bottle.

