Prior to initial dosing of Lazanda, subjects will be instructed on the proper use of the study drug product, according to the instructions in **Section 4.2**. Study subjects will receive an initial supply of Lazanda, 1 bottle of 100 mcg spray, at the time of radiation therapy simulation for use during initial dose titration. A single bottle of Lazanda with increments of 100 mcg sprays will provide 8 doses. Subjects will receive additional supply of Lazanda bottles, 5 mL bottles of 100 mcg or 400 mcg or combination of both, at the first radiation treatment visit as determined by the investigator based on opioid needs and the dose established during titration procedures. If the response to the titrated Lazanda dose markedly changes, an adjustment of dose may be necessary to ensure that an appropriate dose is maintained, and may require a refill supply during the course of radiation treatment as determined by dose adjustment and in discussion with the Principal Investigator. All doses will be carefully monitored and recorded and participants will not receive surplus bottles.

Storage and stability: Lazanda will be stored at up to 25C in the Moores Cancer Center Investigational Drug Services (IDS). Do not freeze. Bottles for individual patient use will be returned to the child-resistant container and in the carbon-lined pouch in the cardboard carton for secure storage at home after each use. Lazanda must be stored out of reach of children and protected from light.

Preparation: Bottles containing Lazanda will be supplied in ready-to-use form. No further drug preparation (e.g., reconstitution, dilution) is required by IDS prior to labeling and dispensing.

Route of administration for this study: Lazanda will be administered as an intranasal spray. Each actuation on the metered-dose nasal spray counter is designed to deliver a spray of 100 mcL of solution containing 100 mcg or 400 mcg fentanyl base. This enables doses of 100 mcg or 400 mcg to be administered using a single spray into one nostril (100 mcg), a single spray into each nostril (200 mcg), or two sprays into each nostril (400 mcg), based on the effective and tolerable dose determined through titration steps described in **Section 4.2**.

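### The half-dose restart after Grade 3 somnolence cannot be given at 100 mcg, or a second time from 200 mcg, and the limit on dose reductions does not cover either case

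*Combined protocol and SAP*

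**What the plan says.** Section 4.7 has four toxicity tables. Those for nausea and vomiting, constipation and urinary retention (Tables 2 to 4) restart the drug at an unchanged dose after Grade 2 or Grade 3. Table 5, for somnolence, is the only one that calls for a reduction. Its Grade 3 row reads "Hold until < Grade 2. Resume at half dose", with no floor and no exception by dose level. A sentence after the tables sets the limit: "Patients requiring a delay of greater than 2 weeks or greater than 2 dose reductions in Lazanda dose for any toxicity should discontinue protocol therapy".

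The doses are set elsewhere:

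- Section 1.2: "A 100 mcg dose is the initial dose of Lazanda for all patients".
- Section 4.2.1: at simulation, "subjects will receive an initial dose of 100 mcg (1 spray) of Lazanda in one nostril". The titration table there lists three doses, 100, 200 and 400 mcg, the lowest given as "1 x 100 mcg spray". The lowest dose that works at simulation is carried into the radiation fractions.
- Section 8.1: each actuation is "designed to deliver a spray of 100 mcL of solution containing 100 mcg or 400 mcg fentanyl base".
- Appendix H: the patient's drug diary explains the same three doses and no others.

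Sections 4.2.1 and 8.1 also allow a later change of dose if the response changes markedly, without saying in which direction. Section 4.8 lists general reasons for ending treatment, including unacceptable adverse events and the investigator's view that safety is at risk. Section 10.6 leaves removal from treatment after a related adverse event to the investigator's judgment.

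**The concern.** A halving rule needs a dose below the current one that the product can deliver. At 100 mcg there is none. Every patient starts there, and anyone for whom 100 mcg is enough stays there for all fractions. The only reduction rule in section 4.7 therefore fails at the lowest level of the dose ladder. The natural place to look for the missing instruction is the limit on the number of reductions, so the question is whether that limit has been met when the impossible step comes up.

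What is at stake is consistent handling of a serious opioid toxicity. Two patients at 100 mcg with the same event could be managed differently with no written rule to say which course follows the protocol. It would also be unclear whether restarting at 100 mcg counts as a deviation.

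**Working it through.** No sample-size or power figure is involved. The check is whether each halving lands on a dose the product can deliver, and how many reductions have been required by the time it does not.

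**Inputs.** Listed doses: 100, 200 and 400 mcg (section 4.2.1). Spray strengths: 100 or 400 mcg (section 8.1). Sprays per bottle: 8 (sections 4.2.1 and 8.1). Reduction rule: new dose = current dose / 2 (Table 5). Limit: discontinue when more than 2 reductions are required, that is, at the third (section 4.7).

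**Check of the inputs against the plan's own figures.** Doses per bottle = 8 / (dose / spray strength):

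- 100 mcg from 100 mcg sprays: 8 / 1 = 8
- 200 mcg from 100 mcg sprays: 8 / 2 = 4
- 400 mcg from 100 mcg sprays: 8 / 4 = 2
- 400 mcg from 400 mcg sprays: 8 / 1 = 8

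All four agree with section 4.2.1, so the spray strengths and dose levels are read correctly.

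**Repeated halving from each titrated dose, with no increase in between:**

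| Titrated dose | Deliverable path | Deliverable halvings | Next half dose | Reduction number of that step | More than 2 required? |
|---|---|---|---|---|---|
| 100 mcg | 100 | 0 | 100 / 2 = 50 mcg | 1 | No |
| 200 mcg | 200, 100 | 1 | 100 / 2 = 50 mcg | 2 | No |
| 400 mcg | 400, 200, 100 | 2 | 100 / 2 = 50 mcg | 3 | Yes |

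The 50 mcg step is half of the smallest spray, and the 400 mcg bottle does not help.

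**Reading the table.** From 400 mcg the two rules fit together: two halvings can be given, and when a third is required the limit ends protocol therapy. From 100 and 200 mcg the undeliverable step arrives before the limit applies. The plan then calls for a dose that does not exist, and its reduction limit gives no alternative. What remains is the general discretion in sections 4.8 and 10.6.

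**The case against.** The strongest case on the other side is that the plan still gives usable instructions and that the gap is narrow. For Grade 3 somnolence at 100 mcg, the hold can be carried out, and so can the prompt investigator review that Table 5 recommends. Sections 4.8 and 10.6 let the investigator end treatment. The trigger is restricted too: Grade 3 drug-related somnolence, followed by recovery and an intention to re-dose, in a trial planned for about 6 patients (Study Summary and section 9.2; section 4.1 says about 15) with at most 10 fractions each. A second reduction from 200 mcg needs repeated Grade 3 episodes within that short course.

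Most of this stands, and it limits the point to the restart step. It does not remove it. Discretion to stop a patient does not say what follows when the table directs a restart at an undeliverable dose, and no other section supplies that instruction.

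Three stronger readings are tempting, and the documents do not support them:

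- **That the limit on reductions can never be reached.** The sentence covers patients who require more than 2 reductions, not only those who have been given them, so a 400 mcg patient meets it at the third. If the later dose adjustment in sections 4.2.1 and 8.1 includes increases, further deliverable reductions could also accumulate. Nor is a cap that some dose levels do not reach a contradiction in itself.
- **That staff have no instruction at all.** Only the restart is undefined.
- **That comparability of PID15 is materially damaged.** Dose already differs between patients through titration and may change within a patient, and the primary model in section 9.3.1 has no dose term. Nothing shows that this path adds appreciably to that.

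**Conclusion.** The concern holds for the restart step. Table 5 conflicts with the protocol's own dose levels at 100 mcg, and at a second reduction from 200 mcg. In both situations the reduction limit does not yet apply, so what happens after the hold is left to general discretion. From 400 mcg the rule and the limit are consistent.

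The number of patients affected cannot be estimated. Section 8.1 places somnolence among events seen in at least 5% of patients but gives no Grade 3 rate, and the documents do not say what share will be titrated to 100 mcg. Sample size and power are not affected.

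The conclusion assumes that half dose means half of the dose the patient was taking when the event occurred, that doses are given in whole metered sprays of the supplied strengths, and, for the reduction counts, that no increase comes between reductions. The 100 mcg case does not depend on that last assumption when it is the patient's first reduction.

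**What to change.** Reconcile Table 5 and the reduction limit in section 4.7 with the deliverable doses in the section 4.2.1 titration table and in section 8.1. After the change, each of the three dose levels should have a restart instruction after Grade 3 somnolence that can be carried out with the supplied sprays and that agrees with the limit on reductions. The text should also state how reductions are counted if a later dose adjustment intervenes. The clinical team decides the content; no dose or rule is proposed here.

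The cost is amendment wording. The design, the sample size and the analysis do not change.
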